**11. Procedures to Maintain Confidentiality:**

Identified data are entered by a dedicated Research Nurse (STU 102010-064) or a dietitian into a secure computer database. The computer used for this data entry and the database itself are both password-protected and can only be accessed by the research nurse and the physicians listed on the protocol. The database will be kept on a password-protected subdirectory of a designated UTSW network drive. All the data collection sheets are stored in a secure cabinet. Data for study analysis will be de-identified with a link kept on a secure database.

Only members of the research team will have access to the data. Confidentiality will be assured by using encrypted electronic devices for transmission of identified information.

Identifiers will be deleted once data on the same patients have been merged across databases. Data for study analysis will be de-identified with a link kept on a secure database.

Privacy will be maintained by speaking with the parents in quiet tones with only authorized persons present in a private room or behind a screen. Identification of the study subject is done in EPIC.

**12. Potential Benefits:**

Benefits to the patient:

There may or may not be direct benefits to the patient. The researchers cannot guarantee that he or she will benefit from participation in this research. We do not know which group the baby will be in; it is possible that he or she may grow faster if he or she is randomized to individualized nutrition and if measurements of milk nutrients inform the nutritionists and infant formula personnel suggest more fortifier may be helpful. It is

possible that he or she may have less feeding problems if he or she is randomized to standard nutrition. It is possible that the researchers may identify a problem with your baby's growth or blood pressure; if that is the case they will let the mother know. It is possible that being in either arm of the study may reduce the risk for neurodevelopmental delay or metabolic syndrome as an adult.

#### Benefits to the society:

We hope the information learned from this study will benefit others with prematurity or small size for gestational age in the future. Information gained from this research could lead to better growth and neurodevelopment and less metabolic syndrome.

#### **14. Biostatistics:**

The primary outcome variable (growth) will be analyzed by intention to treat (i.e., as randomized). Continuous variables including the primary outcome will be analyzed using Student's t-test or analysis of variance and a generalized linear model (to determine the effect of the intervention while taking into account co-variates and confounding variables). Dichotomous variables will be analyzed using chi-square analysis and by estimating relative risk using robust Poisson regression in a generalized estimating equation model. Subgroup analyses will be done to compare the 3 strata (AGA 23-28 weeks, SGA 23-28 weeks and SGA 29-34 weeks) and to compare SGAs due to insufficient calories (e.g., preeclampsia, low placental insertion) vs. constitutionally small neonates (e.g., congenital infection, genetic anomaly, short parents). A probability value  $<0.05$  will be considered statistically significant. Secondary outcome variables will be analyzed according to appropriate statistical techniques.

Sample size analysis: Based on the number of patients delivered at Parkland during the last 10 years, we expect that 342 (1140x3/10) eligible neonates will be delivered over 3 years. We anticipate enrolling half in the study and expect that 2/3 will survive to 36 weeks PMA. Thus we will enroll 150 patients to yield a 100 patients available for the primary outcome and to have 80% power using 2-tailed Student t-test (alpha error 0.025) to detect an increase in weight gain velocity in the NICU by  $2 \text{ g} \times \text{kg}^{-1} \times \text{day}^{-1}$  (standard deviation  $3 \text{ g} \times \text{kg}^{-1} \times \text{day}^{-1}$ ) and 95% power (alpha error 0.001) to detect an increase in length velocity by 0.2 cm per week (standard deviation 0.2 cm per week), taking into account clustering due to twins and multiples. We will have  $>80\%$  power for both outcomes (alpha error 0.05).

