### *Randomization:*

Following parental consent, infants will be double blind randomized with 1:1 allocation using a stratified permuted block design by computer, using opaque envelopes in 3 strata: AGA 23-286/7 weeks, SGA 23-286/7 weeks and SGA 29-346/7 weeks. Twins and multiples will be randomized to the same arm of the study.

*Blinding:* Only the dietitian, infant formula technician and a statistician will be aware of the allocation. The other members of the research team, the care givers and the parents will not know the allocation.

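### Siblings are allocated together, but section 14 names no method for sibling correlation in the continuous primary growth outcomes

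*Combined protocol and SAP*

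**What the plan says.** Under Randomization in section 4: "Twins and multiples will be randomized to the same arm of the study". For multiples, the family is therefore the unit of allocation.

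Section 14 sets the analysis of the two growth velocities: "Continuous variables including the primary outcome will be analyzed using Student's t-test or analysis of variance and a generalized linear model". The generalized linear model is there to estimate the intervention effect while "taking into account co-variates and confounding variables". It has no family term, random effect or cluster-robust variance, and the plan does not say whether the t-test, the analysis of variance or the model decides the primary result. The only correlated-data method, "robust Poisson regression in a generalized estimating equation model", is in the sentence on dichotomous variables, without a stated cluster unit.

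The sample-size paragraph gives "80% power using 2-tailed Student t-test (alpha error 0.025) to detect an increase in weight gain velocity in the NICU" and "95% power (alpha error 0.001) to detect an increase in length velocity by 0.2 cm per week", both said to be "taking into account clustering due to twins and multiples". It gives no multiple-birth share, ICC or design effect. It plans 150 infants to yield 100 for the primary outcome, because the authors "expect that 2/3 will survive to 36 weeks PMA".

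**The concern.** An infant-level t-test or analysis of variance treats all 100 infants as independent. Siblings always share an arm, so a positive correlation in their growth makes the variance of the difference between arms larger than the test assumes. Enrolling more infants to allow for this protects power but leaves the standard error uncorrected. The point estimate is not materially affected; the P value and the confidence interval are.

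A borderline primary result could therefore depend on whether siblings were taken into account. Section 1 describes the trial as groundwork for a later multicentre trial. That limits the consequence, but it also means that an estimate of sibling correlation would be useful, and the analysis as written would not produce one.

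**Working it through.** **Inputs from section 14.** 50 infants per arm; weight difference 2 with SD 3 (d = 2/3), two-sided alpha 0.025; length difference 0.2 with SD 0.2 (d = 1), alpha 0.001, taken here as two-sided.

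**Assumed, because the documents do not give them.** Share of infants who are twins 0.2-0.4; sibling ICC 0.3-0.7; pairs only.

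**Step 1: the plan's own power figures, without clustering.**
- Weight: 85.3% (noncentral t) or 86.3% (normal approximation), against 80% stated.
- Length: 94.2% (t) or 95.6% (normal), against 95% stated.

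**Step 2: the design effect (DE) that each figure implies.** With effective n per arm = 50/DE:
- 80% for weight needs DE 1.135 (t) to 1.169 (normal).
- 95% for length needs DE 0.972 (t) to 1.026 (normal), which leaves almost no room for clustering.

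With two-sided tests, no single DE gives both figures exactly. At DE 1.14, length power is 89.3% (t) or 91.8% (normal).

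**Step 3: plausible design effects.** DE = 1 + share × ICC × q, where q is the chance that an analysed twin's sibling is also analysed. Three cases:
- *Every pair complete, q = 1.* DE = 1 + 0.2 × 0.3 = 1.06, up to 1 + 0.4 × 0.7 = 1.28.
- *Siblings lost independently, q = 2/3* (the plan's expected survival). DE = 1.04 to 1.19.
- *Independent loss and no complete pairs in SGA 29-34 weeks*, since section 5 admits that gestational age only if the infant is SGA. The Table 3 counts for weight gain velocity (470 AGA and 48 SGA below 29 weeks, 355 SGA at 29-34 weeks) put 518/873 = 0.593 of infants in the strata that can hold pairs, if multiples are equally common across strata. Then q = 2/3 × 0.593 = 0.396 and DE = 1.02 to 1.11.

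**Step 4: effect on the unadjusted test.** True alpha = 2 × (1 − Φ(1.96/√DE)); interval shortfall = 1 − 1/√DE.

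| Case | DE | True alpha at nominal 0.05 | Intervals too narrow by |
|---|---|---|---|
| Loss, no SGA 29-34 pairs | 1.02-1.11 | 0.053-0.063 | 1-5% |
| Independent loss | 1.04-1.19 | 0.055-0.072 | 2-8% |
| All pairs complete | 1.06-1.28 | 0.057-0.083 | 3-12% |

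**Step 5: simulation.** 100 infants, pairs allocated together, blocks of 4 in three strata, Table 3 means and stratum mix, 8000 runs per cell (Monte Carlo SE about 0.0025). Here the SGA 29-34 week restriction was applied without independent loss. Every simulated pair lay in one stratum. Ranges of t-test alpha at nominal 0.05:

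| Outcome and SD | All pairs complete | Independent loss | No SGA 29-34 pairs |
|---|---|---|---|
| Weight, SD 3 | 0.051-0.086 | 0.056-0.075 | 0.054-0.070 |
| Length, SD 0.2 | 0.050-0.070 | 0.046-0.066 | 0.041-0.064 |
| Length, Table 3 SDs | 0.054-0.077 | 0.053-0.069 | 0.049-0.053 |

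A linear model with strata and a small-sample-corrected (CR2) family-robust variance gave 0.045-0.058 over all weight and length cells (2500 runs each, SE about 0.0044).

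**Step 6: power once siblings are accounted for (noncentral t).**
- DE 1.02-1.11: weight 84-81% at alpha 0.025; length 93-90% at alpha 0.001.
- DE 1.28: weight 74%; length 83%.
- At alpha 0.05, even with DE 1.28: weight 83%, length 99%.

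**The case against.** The strongest defence is that the plan is not blind to clustering. It names twins and multiples in the power statement and GEE for dichotomous outcomes, and a generalized linear model can carry a GEE or robust variance. A reader might infer that the authors mean to ignore siblings; the text does not support that. What stands is a gap in specification: the extension is not stated, the model is not named as primary, and the plain t-test remains available.

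A reader might also infer that the two power figures contradict each other, or that only a near-zero ICC for length could explain them. Neither follows. Different ICCs for the two outcomes are one explanation. If 80% is a floor, a single DE up to 1.026 meets both figures (weight 85.3%, length 95.0%, normal approximation). The two-tailed label is attached to the weight test; if length was one-sided, a single DE near 1.12 gives about 81.8% and 94.9%. The fair statement is that the allowance cannot be checked.

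On size, the upper values need 40% multiples, ICC 0.7 and every pair complete, which sits badly with the expected survival and the SGA restriction. That objection stands, so the low range is the better guide, although positively correlated sibling survival would raise it. For length, the simulated alphas include values at or below nominal. That stands too.

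**Conclusion.** The omission is clear from the text: multiples are allocated as families, and no sibling-level method is given for either primary growth velocity. If the infant-level t-test is used and sibling growth is positively correlated, its standard error is generally too small.

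Confidence in the size is low. It rests on an assumed multiple-birth share and ICC, pairs only, and the loss patterns above. The effect is probably modest for weight and may be absent for length. The fully paired case is an upper limit within the assumed range and should not be read as the expected value.

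A reader might take this to mean that 100 evaluable infants are too few. The documents do not support that. In the case that combines both reductions, weight power stays at or above the stated 80%, and the claim of more than 80% power at alpha 0.05 holds for each outcome across the whole assumed range. Given the trial's preparatory purpose and the cheap remedy, this should be fixed, but it does not undermine the design.

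**What to change.** In section 14, for each growth velocity, name as primary one linear model that accounts for clustering by mother. Either GEE or cluster-robust variance with a small-sample correction, or a random intercept for mother, would serve. Include arm and the randomisation strata as fixed effects, and keep the t-test as descriptive. Report the estimated sibling ICC for use in the later trial.

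In the sample-size paragraph, state the multiple-birth share, the ICC for each outcome and the sidedness of each test, and restate the two power figures on that basis without changing the sample size.

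The cost is one paragraph and a revised power statement, with no change to conduct. Intervals become √DE − 1 wider than the unadjusted ones: about 1-5% in the case that combines both reductions and 13% at DE 1.28. The restated power may be less favourable: length may fall below 95% at alpha 0.001, and weight below 80% at alpha 0.025 if DE exceeds about 1.14-1.17.

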Purpose: To provide preliminary data for a multicenter randomized trial to test whether individualized and optimized nutrition in ELGANS and SGA preterm neonates improves neurodevelopmental outcomes and reduces the risk of metabolic syndrome. This could be of major public health significance.

Standard of care: Feeding human milk rather than formula has several advantages for preterm infants including decreasing the frequency of necrotizing enterocolitis and infections. However, human milk does not provide enough calories or proteins, leading to less growth; therefore, human milk must be supplemented with human milk fortifier, and for some babies, additional protein or fat. The amount of protein and fat in mother's breast milk and donor milk is highly variable, often leading to insufficient growth velocity. There are three ways to fortifying human milk for preterm infants: (1) Standard, fixed dosage fortification; (2) Adjustable (optimized) fortification using growth velocity to modify caloric supplementation and a surrogate for protein sufficiency to modify the dosage of protein fortification, and (3) Targeted (customized, individualized) fortification or fortification triggered by poor growth and results from human milk analysis. One small randomized trial showed that growth of preterm infants in the NICU improved using adjustable supplementation of human milk based on weekly BUN levels. Other authors have used this approach and observed better growth without any toxicity. At Parkland we have used this approach for more than a decade: adjustment of human milk fortification is based on growth velocity and weekly serum BUN and albumin levels; protein intake is increased weekly until BUN is greater than 10 mg/dl and albumin is  $> 3$  g/dl.

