#### Other measurements:

- Maternal pre-pregnancy weight, height, body mass index (BMI), weight gain during pregnancy, placenta weight, antenatal and perinatal maternal diseases (e.g., diabetes mellitus, preeclampsia), antenatal steroids, intrauterine growth restriction
- GA: best obstetrical estimate (if no prenatal care, new Ballard score)
- Race/ethnicity, insurance, socioeconomic status, maternal education
- Birth & 36 weeks measurements: weight, FOC, length (obtained on stadiometer within 3 days of birth; up to 7 days of life in patients who are initially critical and unstable), BMI (using BW and length on stadiometer to improve accuracy), abdominal circumference, mid-arm circumference

- Comparison of relative changes [(36-week measurement – birth measurement)/birth measurement] in weight, length and FOC from birth to 36 weeks PMA; change in z score in weight, length and FOC
- Serial measurements of weight, length (using stadiometer for calculating BMI), linear growth estimated from the percent change of heel-knee height measurements in the critically ill unstable neonate, FOC, arm and thigh muscle circumference, abdominal circumference
- At discharge: triceps and subscapular skinfold thickness
- Nutritional tests: weekly BUN adjusted if necessary for renal dysfunction (see study intervention), albumin, electrolytes, phosphate, alkaline phosphatase; if the latter two tests suggest osteopenia: bone radiogram; vitamin D levels will be considered in severe cases.
- Days without feeding, human milk vs. formula, days to full feeds, days of central line & parenteral nutrition, refeeding syndrome, metabolic acidosis, osteopenia of prematurity, micronutrient deficiency (e.g. zinc, essential fatty acids, carnitine), mineral deficiency (e.g., magnesium), type and composition of feeding at discharge
- Morbidities affecting growth or neurodevelopment, e.g., congenital infection, genetic anomaly, organ failure, bronchopulmonary dysplasia, antibiotics/sepsis, major surgery, intestinal perforation, necrotizing enterocolitis, severe intraventricular hemorrhage, periventricular leukomalacia, congenital anomalies, systemic steroids
- Cumulative percentage of enteral intake as breast milk in the NICU, which may influence the effect of the intervention and glucose, lipid and apolipoprotein metabolism.

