#### **4. Study Procedures:**

### *Screening:*

Screening for potential candidates for the RCT will be done by the investigators who will run the quality improvement project that started in May 2015: Optimizing Individual Nutrition in Preterm Very Low Birth Weight Infants (STU 102014-045).

Nutrient intake is decided by the clinical care team with recommendations by dietitians, using published data on breast milk composition, published recommendations, weekly rate of growth, feeding tolerance and measurements of serum BUN ( $> 10$  mg/dl), albumin ( $> 3$  g/dl), electrolytes, phosphate and alkaline phosphatase and bone radiograms as needed. Weight and length at birth were previously obtained by nurses and classified using 1963 Lubchenco's growth curve. Size after birth was assessed using the 2003 Fenton's growth curve, length curve including crown-heel measurements (obtained by nurses using paper tape or dietitians using a stadiometer) and height calculated from heel-knee height, mid-arm circumference and abdominal circumference.

New curves have become available on EPIC: weight, length and FOC in 2015 and BMI in 2016. The research team have implemented 2010 Olsen's curve for birth and subsequent measurements up to 39-40 weeks, 2013 Fenton's curves up to 50 weeks PMA, and WHO curves starting at 40-41 weeks), 2015 Holston's (BMI), and serial anthropometric measurements to compare growth parameters with expected values at each stage. Weight gain velocity will be calculated as described by Patel. Linear growth in critical unstable infants will be followed using heel-knee height. BMI will be calculated using only lengths measured on a stadiometer or an infantometer. Nutrition will be optimized using serum BUN goals with adjustment for serum creatinine levels compared to normal values for age. This approach will be standard care, which will be the intervention in any patient entered in the RCT.

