## **5. Criteria for Inclusion of Subjects:**

Patients born at Parkland Hospital & Health System

Gestational age < 29 weeks or gestational age < 35 weeks and small for gestational age

Maternal plan to breastfeed or to use milk from the milk donor bank From birth to 1 week of life

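### The power stated for length velocity uses an SD of 0.2 cm/week, which the protocol's own Table 3 supports only for infants under 29 weeks, not for the eligible SGA 29-34-week stratum (SD 0.6)

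*Combined protocol and SAP*

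**What the plan says.** Section 14 (Biostatistics, sample size analysis) plans 150 enrolled infants to obtain 100 with the primary outcome. Weight velocity is powered "using 2-tailed Student t-test (alpha error 0.025") for a difference of 2 g/kg/day with SD 3. For length velocity the section claims "95% power (alpha error 0.001) to detect an increase in length velocity by 0.2 cm per week (standard deviation 0.2 cm per week"). It adds more than 80% "power for both outcomes (alpha error 0.05"), and says that clustering of twins and multiples is allowed for. It gives no source for the length SD, no intraclass correlation, no multiple-birth rate and no design effect.

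Section 5 defines the population: "Gestational age < 29 weeks or gestational age < 35 weeks and small for gestational age". Under Randomization in section 4, and again in the subgroup plan of section 14, there are three strata: AGA 23-28 weeks, SGA 23-28 weeks and SGA 29-34 weeks. No expected share or cap is given for any of them.

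**The concern.** One SD is applied to all 100 evaluable infants, although the protocol's retrospective data show that linear growth is three times as variable in one of the three strata. Table 4 points the same way: its SD for VLBW infants, a partly different population, is 0.4, twice the planning value.

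Length velocity is one of the two primary growth measures, and the trial is meant "To provide preliminary data for a multicenter randomized trial". If length velocity does not differ between arms, readers will set that result against a stated power of 95%. If true power is nearer two in three, the null result will be taken as much stronger evidence against an effect than it is.

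**Working it through.** **Inputs.** Difference 0.2 cm/week, 50 per arm (100 evaluable, 1:1), two-sided Student t-test (section 14; the test is named for weight and read as applying to length). Linear growth velocity, Table 3, mean ± SD (n):
- under 29 weeks AGA: 1.0 ± 0.2 (459)
- under 29 weeks SGA: 1.0 ± 0.2 (47)
- 29-34 weeks SGA: 0.9 ± 0.6 (354)

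**Reproducing the plan.** The noncentrality is 0.2 / (SD × √(2/50)) = 1/SD, with 98 degrees of freedom. For SD 0.2 it is 5.0. Power at alpha 0.001 is 94.2% (noncentral t), or 95.6% by the normal approximation (5.0 − 3.29 = 1.71). At 0.05 it is 99.9%. The stated 95% is reproduced before any clustering.

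**Pooled SD.** With share p of SGA 29-34 weeks:

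variance = (1−p) × 0.2² + p × 0.6² + p(1−p) × (1.0−0.9)²

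**Share.** The plan states none, so p is an assumption. The documents offer two reference points:
- 354/(459+47+354) = 354/860 = 41%, among eligible infants discharged home (Table 3).
- 354/1140 = 31%, using the ten-year count behind "we expect that 342 (1140x3/10) eligible neonates will be delivered over 3 years". This assumes that both counts cover the same ten years. It also divides infants discharged home by births, so it probably understates the share among survivors.

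At 41%: 0.588 × 0.04 + 0.412 × 0.36 + 0.588 × 0.412 × 0.01 = 0.174, SD 0.417. 
At 31%: 0.689 × 0.04 + 0.311 × 0.36 + 0.689 × 0.311 × 0.01 = 0.142, SD 0.376.

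**Power before clustering (noncentral t)**

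| Share of SGA 29-34 wk | Pooled SD | alpha 0.05 | alpha 0.025 | alpha 0.001 |
|---|---|---|---|---|
| 0% | 0.200 | 99.9% | 99.6% | 94.2% |
| 3% | 0.223 | 99% | 98% | 86% |
| 5% | 0.238 | 99% | 97% | 79% |
| 10% | 0.270 | 96% | 92% | 62% |
| 20% | 0.325 | 86% | 79% | 38% |
| 26% | 0.354 | 80% | 71% | 29% |
| 31% | 0.376 | 75% | 65% | 24% |
| 41% | 0.417 | 66% | 55% | 17% |

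Simulating the mixture with a pooled t-test gives 67% and 18% (alpha 0.05 and 0.001) at a 41% share, and 76% and 26% at 31%, so the non-normal mixture does not change the picture.

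**Thresholds.** 80% at 0.05 needs a pooled SD of at most 0.353, that is p ≤ 25.9%. 80% at 0.025 needs at most 0.320, p ≤ 19.1%.

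**Sensitivity**
- *Rounding of the Table 3 SDs* (0.15-0.25 and 0.55-0.65): the 26% threshold moves between about 17% and 36%. Power at 0.05 is 57-75% at the 41% share and 65-84% at 31%. At 0.001 it is 12-24% and 16-35%.
- *Clustering* (assumed design effects 1.05 to 1.3, using 50/design effect per arm): power at 0.05 is 64% to 55% at the 41% share and 73% to 63% at 31%. Even with SD 0.2 throughout, power at 0.001 falls to 93%-83%.
- *Table 4 SD of 0.4 for everyone:* 70% at 0.05.

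**Weight velocity.** The same pooling of Table 3 gives SD 2.6, below the planned 3; SD 3 gives 85% at 0.025. That calculation is not affected.

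**The case against.** The strongest reply is that Table 3 may not describe the trial. It runs from birth to discharge, not to 36 weeks PMA. Earlier lengths were "obtained by nurses using paper tape or dietitians using a stadiometer", whereas the trial specifies "length (obtained on stadiometer within 3 days of birth", allowing up to 7 days for unstable infants. The trial also excludes infants too unstable for an accurate length and those with major congenital abnormalities, and requires planned human milk. All this could lower the SD. It stands as a caution on any single power figure: an SD in the SGA 29-34-week stratum of 0.49 (41% share) or 0.55 (31% share) would restore 80% at 0.05, and the second is close to rounding error. It does not rescue the 0.001 claim. Even an SD of 0.2 in that stratum gives 92-93%, because of the 0.1 difference in means, and no section argues for so low a value.

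Second, the plan also names a generalized linear model. Adjusting for stratum removes only the difference in means and moves power at the 41% share from 66.0% to 66.6%. Weighting strata by inverse variance would help: the information is 0.588 × 50/(2 × 0.04) + 0.412 × 50/(2 × 0.36) = 368 + 29 = 396 (unrounded), a standard error of 0.050, and power of about 98% at 0.05 and 75% at 0.001. But the plan specifies no such weighting, its stated power is for a t-test, and about 93% of the weight (368/396) would fall on infants under 29 weeks.

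Third, significance is declared at 0.05, so alpha 0.001 governs no decision. That is true and limits the harm, but the figure remains a claim about a primary measure.

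**Conclusion.** The concern holds and should be fixed. It is an unsupported planning input, not a calculation error.

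Two conclusions are firm. The SD of 0.2 has no stated source and conflicts with Table 3 for one eligible stratum. And 95% power at alpha 0.001 has no margin: with the Table 3 SDs it drops to 86% at a 3% share and is at most 35% at either reference share, even with favourable rounding.

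The failure of 80% at 0.05 is conditional. At the 41% share it fails across the whole rounding range (57-75%). At 31% it fails at the central SDs (75%) but could survive at the favourable end (84%). At the central figures, the planned t-test would miss a true difference of 0.2 cm/week about one time in three or one in four, against the stated less than one in five. All of this assumes 50 evaluable infants per arm and that historical SDs and shares carry over. Any design effect above 1 makes it worse.

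**What to change.** 1. Withdraw the claim of 95% power at alpha 0.001.
2. Restate length power with an SD pooled over the three eligible strata. State the assumed share of each stratum, the source of each SD, and the design effect with its basis. With Table 3 SDs and before clustering, this gives about 66% at 0.05 and 55% at 0.025 for a 41% share. A 31% share gives about 75% and 65%, but mixes infants discharged home with births, so 41% is the closer proxy for evaluable infants.
3. Keep the statement of more than 80% power for both outcomes only if the declared inputs give a pooled length SD of at most about 0.35, and less after clustering. Otherwise confine it to weight velocity.

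The cost is protocol wording only: no extra infants and no change to the analysis. The sponsor would have to accept a less favourable stated power for length and commit to stratum shares and a design effect that are now unstated.

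### The 95% power for length velocity is essentially the figure without clustering, and the claim of more than 80% power for both outcomes fails for length at the case mix in Table 3

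*Combined protocol and SAP*

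**What the plan says.** Section 14 (Biostatistics), sample size analysis, plans as follows: "Thus we will enroll 150 patients to yield a 100 patients available for the primary outcome". On those 100 infants it makes three power statements.

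- Weight: "80% power using 2-tailed Student t-test (alpha error 0.025"), "to detect an increase in weight gain velocity in the NICU by" 2 g/kg/day, with SD 3 g/kg/day.
- Length: "95% power (alpha error 0.001) to detect an increase in length velocity by 0.2 cm per week", with SD 0.2 cm per week.
- Both outcomes: more than 80% power at alpha 0.05, the significance level that the section sets.

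The sentence with the weight and length figures ends by saying that they were obtained "taking into account clustering due to twins and multiples". The Randomization paragraph in section 4 gives 1:1 allocation and adds: "Twins and multiples will be randomized to the same arm of the study". No twin share, intraclass correlation (ICC) or design effect appears anywhere.

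Table 3 (Preliminary Retrospective Data) gives linear growth velocity for the three strata that the trial enrols: 1.0±0.2 cm/week (below 29 weeks AGA, n = 459), 1.0±0.2 (below 29 weeks SGA, n = 47) and 0.9±0.6 (29–34 weeks SGA, n = 354).

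**The concern.** Two things in the length figure look too favourable.

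First, 95% is close to what 100 independent infants would give. If clustering had been taken off, the result should be visibly lower, as the weight figure is: 80% stated against about 85% for independent infants.

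Second, the SD of 0.2 fits the two strata below 29 weeks but not the 29–34-week SGA stratum, where the protocol's own SD is three times as large.

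Length velocity is named in the primary hypothesis and the primary endpoint. If its real power is well below the stated figure, a null length result would be read as stronger evidence of no effect than it is. The trial is also meant to supply preliminary data for a multicentre trial, which would inherit the same planning SD.

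**Working it through.** **Inputs.** 50 evaluable infants per arm (100 at 1:1). Length: difference 0.2, SD 0.2, standardised effect 1.0, alpha 0.001. Weight: difference 2, SD 3, standardised effect 0.667, alpha 0.025. Tests are two-sided. All come from section 14.

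**Formula.** Power = P(T > t(1−α/2; 2n−2)), where T is noncentral t with 2n−2 degrees of freedom and noncentrality (difference/SD)×√(n/2). For a design effect DE, n is replaced by 50/DE.

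**Step 1: the plan's figures without clustering.**
- Length: noncentrality 1.0×√25 = 5.0, critical t 3.39, power **94.2%**. Normal approximation: Φ(5.0 − 3.29) = 95.6%. Both are close to the stated 95%.
- Weight: noncentrality 0.667×5 = 3.33, power **85.3%** (normal 86.3%). The stated 80% leaves room for a design effect.

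**Step 2: effect of clustering** (t-test, normal approximation in brackets).

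| Design effect | n per arm, effective | Length, alpha 0.001 | Weight, alpha 0.025 |
|---|---|---|---|
| 1.00 | 50.0 | 94.2% (95.6%) | 85.3% (86.3%) |
| 1.05 | 47.6 | 92.6% (94.4%) | 83.3% (84.4%) |
| 1.10 | 45.5 | 90.8% (93.0%) | 81.4% (82.6%) |
| 1.20 | 41.7 | 86.9% (89.9%) | 77.5% (78.9%) |

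**Step 3: are the two figures compatible?** If weight power is exactly 80%, the effective n per arm is 44.1 and DE = 50/44.1 = 1.13. If length has the same DE, its power is about **90%** (89.5% by t). By normal approximation the DE is 1.17 and length power 90.9%. This step rests on two assumptions: that 80% is exact, and that both outcomes share one DE.

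**Step 4: the SD.** Pooling the Table 3 variances within strata:

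(458×0.2² + 46×0.2² + 353×0.6²)/857 = (18.32 + 1.84 + 127.08)/857 = 0.172, so SD = **0.41**.

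Table 4 gives 0.4 for all infants below 1500 g, which is not the eligible population but is of the same size. Length power by t-test at alpha 0.05:

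| SD | No clustering | DE 1.13 |
|---|---|---|
| 0.20 | 99.9% | 99.6% |
| 0.40 | 69.7% | 64.3% |
| 0.41 (0.414) | 66.6% | 61.2% |

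**Step 5: dependence on case mix.** With a share p of 29–34-week SGA infants, the variance is (1−p)×0.04 + p×0.36 = 0.04 + 0.32p.
- No clustering: 80% power needs SD ≤ 0.353, so p ≤ (0.353² − 0.04)/0.32 ≈ 27%.
- DE 1.13: SD ≤ 0.332, p ≤ 22%.
- DE 1.2: SD ≤ 0.322, p ≤ 20%.

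The historical share in Table 3 is 354/860 = 41%.

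**Step 6: weight on the same basis.** At alpha 0.05 with SD 3, weight power is 91.0% without clustering and 87% at DE 1.13. The Table 3 weight SDs (1.9, 2.4, 3.3; n = 470, 48, 355) pool to √[(469×1.9² + 47×2.4² + 354×3.3²)/870] = 2.6, below the planning value of 3. Only the length assumption is optimistic.

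**The case against.** The strongest reply on clustering is that 94.2% and 95.6% bracket 95%, so the plan's figure does reproduce and a gap of 0.8 points in a rounded planning number is not an error. That is right for the calculation without clustering.

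A reader might go further and infer that the length figure cannot include clustering at all, or that true power is 90%. The documents do not support either. The 80% for weight may be a floor, and weight and length may have different ICCs. By normal approximation a design effect of 1.02 still gives 95.2% for length with weight above 80%. A one-sided t-test would give 95.2% at 1.05, but the paragraph names a two-tailed test. What stands is narrower: under the named test no design effect above 1 reaches 95%, and the reader cannot tell what allowance was made.

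It is also true that alpha 0.001 decides nothing in this plan. At SD 0.2 and alpha 0.05, length power is about 99% even at a design effect of 1.3. On the clustering point alone, neither the sample size nor any conclusion would change.

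On the SD, the sponsor can say that 0.2 is exactly the Table 3 value below 29 weeks, that Table 3 follows infants to discharge while the endpoint stops at 36 weeks PMA, and that the enrolled mix may contain fewer 29–34-week infants. An analysis that weights strata by precision could also recover some power. These points limit how firmly 67–70% can be asserted. They do not justify 0.2 for a trial that enrols all three strata without stating the expected mix.

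**Conclusion.** The point holds, in two parts of unequal weight.

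- **Clustering.** The stated 95% is essentially the power for 100 independent infants. With siblings in one arm and positive within-family correlation it is lower: about 93%, 91% and 87% at design effects of 1.05, 1.1 and 1.2 (t-test, SD 0.2). About 90% follows only if the weight figure is exact and both outcomes share a design effect. This is an unverifiable and slightly generous statement, with little practical effect.
- **SD.** At the Table 3 case mix the pooled SD is about 0.41. Length power at alpha 0.05 is then about 67–70% without clustering, or 61–64% at a design effect of 1.13. The statement of more than 80% power for both outcomes fails for length at that mix. It survives if the 29–34-week SGA share is about 20% or less. This part rests on Table 3 SDs applying to the trial's measurement window and on an unweighted comparison.

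A reader might conclude that the trial is too small. That does not follow: weight is adequately powered on the plan's own inputs, and length power depends on a stratum mix that the plan has not stated.

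**What to change.** In section 14:

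1. State the assumed share of twins and multiples, the ICC and the resulting design effect for each outcome, and recompute the weight and length powers with them. The 1.13 above is back-calculated and should not be written in as if it were known.
2. State the expected stratum mix and give length power at alpha 0.05 with the Table 3 SDs under that mix, alongside the figure at SD 0.2.
3. Reword the closing sentence so that the claim of more than 80% power covers length only under the mix and SD for which it is true.

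No change to the number enrolled, the conduct or the analysis is needed for this point. The cost is a few sentences and a less favourable stated power for length.
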